12.2.3.10 The prevalence of mucosal breaks

The prevalence of mucosal breaks obtained through upper endoscopy or historical reports and endoscopy findings after the treatment period will be described descriptively and reported in tables.

12.2.4 Safety objectives

Tables and graphs will describe the safety objective descriptively. In addition, the relationship between dose and AE will be evaluated by a logistic regression, using merged AE data from both spontaneous registrations and from active inquiry.

Laboratory data will be analyzed using descriptive statistics. Truncated laboratory values (values below the limit of quantification) will be set to LLOQ in all analyses.

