5.8 Discontinuation of investigational product

Patients may be discontinued from IP in the following situations:

- Patient decision. The patient is at any time free to discontinue treatment, without prejudice to further treatment
- AE
- Severe non-compliance to study protocol
- Incorrectly randomized patient, see Section 5.3
- Development of any of the following study specific criteria for individual patients, which **must** lead to discontinuation of IP:
 - Patient experiencing symptoms of paraesthesia daily for at least 7 consecutive days, see Section 6.4.3.1
 - Patient experiencing a syncopal episode (loss of consciousness) from any cause
 - Patient describing an AE of pre-syncope or dizziness as severe. Orthostatic dizziness provoked during testing would not automatically discontinue a patient unless this continued without provocation from orthostatic testing (eg at home when getting up)
 - Patient with a corrected QT interval (QTcF) ≥ 500 ms
 - Patient with ALT or AST $> 5 \times$ ULN, see Section 6.4.5.2

- Patient with ALT or AST >3 x ULN in combination with BIL >2 x ULN, see Section 6.4.5.2
- Patient with ALT or AST >3 x ULN and clinical signs or symptoms indicating liver dysfunction, see Section 6.4.5.2
- AstraZeneca may decide to stop a dose group in the study based on a recommendation from the DSMB. The following criteria, included in the DSMB charter, serve as a guide for the DSMB to stop a dose group. However, a more restrictive approach may be applied based on the DSMB's and AstraZeneca's evaluation during the study:
 - two or more unique events of syncope in different patients in the same dose group that cannot definitively be attributed to another cause (eg, syncope while having blood drawn would be attributable to the blood draw, not the investigational product)
 - corrected QT interval (QTcF) \geq 500 ms in 20% of the planned total number of patients to be enrolled in the same dose group.
 - dizziness causing discontinuation from the IP in 10% of the planned total number of patients to be enrolled in the same dose group.

If a dose group is stopped, any treatment group(s) on a higher dose will also be stopped.

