If a decision has been taken to stop a dose group the investigator will receive information about which patients (randomization codes) should be discontinued from treatment. The investigator at each site must immediately inform the patient to stop intake of the IP and to schedule an end of treatment visit within 1 week and a subsequent end of study visit. The investigator must also ensure that no new patients will be randomized to the stopped dose group. Patients on lower doses of IP and placebo will continue in the study unless the site is informed otherwise.

In all patients discontinued from the IP, data collection and procedures should continue as described in Section 5.8.1. If the patient does not agree to attend an end of treatment visit, a modified follow up should be arranged (eg, telephone contact to follow-up with respect to any ongoing AEs or a reminder to return the e-diary device and unused IP), if agreed to by the patient and in compliance with local data privacy laws/practices. Relevant information should be recorded in the unscheduled visit section in the eCRF.

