12.2 Methods of statistical analyses

12.2.1 Statistical evaluation – general aspects

The FAS will be used in the efficacy analyses described in this section. Analyses on RESQ-eD data will be based on imputed data. Unless otherwise stated, daily (approximately a 24 h period) values will be used. All patient reported outcome analyses will be calculated by using pooled data from all languages and cultures, if nothing else is stated under each paragraph. A Statistical analysis plan (SAP) will be prepared before unblinding data.

In the event of a dose group being terminated due to safety stopping criteria, the dose group would be excluded from the primary efficacy analyses comparing AZD3355 to placebo but included in safety presentations, PK analyses and the estimations of dose-response curves.

The statistical analysis will be performed by Statistics and Informatics, AstraZeneca R&D Mölndal, using mainly SAS® version 8.2. If available and necessary SAS® version 9.0 will be used.

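### After a safety stop, the logistic regression of AE on dose compares shortened exposure at the top doses with four full weeks elsewhere, and so understates the dose–AE slope

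*Protocol*

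**What the plan says.** Section 12.2.4 describes safety with tables and graphs and adds one model: "the relationship between dose and AE will be evaluated by a logistic regression", using spontaneously reported and actively questioned events together. It states no exposure term, censoring rule or common observation window.

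Section 5.8 sets out what follows a safety stop:

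- "If a dose group is stopped, any treatment group(s) on a higher dose will also be stopped".
- Patients in a stopped group cease IP at once and "schedule an end of treatment visit within 1 week and a subsequent end of study visit".
- Sites must see that "no new patients will be randomized to the stopped dose group".
- For the arms below the stopped dose, the rule is the opposite: "Patients on lower doses of IP and placebo will continue in the study unless the site is informed otherwise".

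The guides for a stop include "two or more unique events of syncope in different patients in the same dose group" and "dizziness causing discontinuation from the IP in 10% of the planned total number of patients".

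Section 12.2.1 takes a terminated group out of the primary efficacy comparison, but the group is "included in safety presentations, PK analyses and the estimations of dose-response curves". Section 12.1.2 puts every dosed patient with any post-dose data in the safety set.

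**The concern.** A yes/no AE outcome depends on how long the patient was at risk. A plain logistic regression treats all patients as observed equally long. After a stop that is untrue in one direction only: patients on treatment at that moment are cut short, and all of them are in the stopped dose or above. Short exposure is then confounded with high dose, and the fitted dose relation is flatter than the true one for AEs that accumulate over treatment.

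Section 1.3 bases the choice of therapeutic dose on efficacy together with safety and tolerability. An error here is in the reassuring direction.

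The point has three limits. The event that triggers the stop is selected upwards by the rule, so it is not reliably understated. AEs at the start of dosing are little affected; section 1.4 says paraesthesia is often over within an hour of a dose. Comparisons among the doses that continue are unaffected.

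**Working it through.** The protocol gives no figure for this regression, so there is none to reproduce.

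**Inputs from the protocol.** 130 patients per arm (12.3); doses 0, 60, 120, 180 and 240 mg bid; four weeks of treatment and two of follow-up; the stopping rules in 5.8.

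**Assumptions, not in the protocol.** Uniform accrual over 20 weeks; constant AE hazard; four-week AE risk on a linear logit of 10, 12.8, 16.1, 20.2 and 25%. The true odds ratio, 240 mg against placebo, is (0.25/0.75)/(0.10/0.90) = 3.0.

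**Formulas.** Four-week cumulative hazard h = −ln(1 − p), which is 0.105 on placebo (h0), 0.226 at 180 mg and 0.288 at 240 mg. For a stop at week t, a stopped arm has 130·t/20 patients, entry uniform on (0, t) and exposure e = min(4, t − entry). Its risk is the mean of 1 − exp(−c), where c is:

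- on-drug AEs only: h·e/4
- placebo-level AEs continuing to week 4: h·e/4 + h0·(1 − e/4)
- AEs counted for w weeks after last dose: h·e/4 + h0·w/4, with w = 2 or 3 after a stop and 2 otherwise

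The logistic model is then fitted to the expected counts.

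**Worked case: 180 and 240 mg stopped at week 8, on-drug AEs.** Each stopped arm has 130 × 8/20 = 52 patients. Half entered by week 4 and have full exposure; for the rest e is uniform on (0, 4), so mean exposure is (4 + 2)/2 = 3.0 weeks. At 240 mg the truncated half has mean risk 1 − 0.25/0.288 ≈ 0.131, so the arm shows (0.25 + 0.131)/2 ≈ 19.0% instead of 25%. At 180 mg the same steps give about 15.3% instead of 20.2%. The fitted odds ratio is 2.05, and ln 2.05/ln 3.0 = 0.65 of the true slope.

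**180 and 240 mg stopped, expected odds ratio:**

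| AE counting | No stop | Week 8 | Week 12 | Week 20 |
|---|---|---|---|---|
| On-drug only | 3.00 | 2.05 | 2.30 | 2.55 |
| Placebo-level AEs to week 4 | 3.00 | 2.42 | 2.58 | 2.73 |
| To 2 weeks after last dose | 2.38 | 1.73 | 1.90 | 2.08 |
| To 3 weeks after last dose if stopped | 2.38 | 1.85 | 1.99 | 2.13 |

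The share of the stopped arms with under four weeks on IP is 50%, 33% and 20% at these weeks.

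**Variations (true odds ratio 3.0):**

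- Only 240 mg stopped, weeks 2–20: 2.31–2.65 on-drug, 2.56–2.78 with placebo-level AEs.
- 70% of the risk in week 1, 180 and 240 mg stopped at weeks 8–20: 2.46–2.75 and 2.67–2.85.
- Accrual of 12–28 weeks, stops at weeks 8–12: 1.98–2.33 and 2.37–2.60. Section 9.5 (Q4 2009 to Q2 2010) allows at most about 39 weeks for the whole study.
- No true dose effect (10% in every arm), on-drug AEs: 0.74, 0.81 and 0.87 for stops at weeks 8, 12 and 20, a spurious protective trend.

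**Very early stops.** At weeks 2–4 the odds ratio would be 1.40–1.54 on-drug, or 1.97–2.07 with placebo-level AEs. The dizziness guide needs 10% of 130 = 13 patients and the QTcF guide 20% of 130 = 26, while only 13–26 patients per arm would have been enrolled. So early a stop is realistic only through the two-syncope guide or DSMB discretion.

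**Stops generated by the protocol's own guides.** 1,200 simulated runs per setting; the AE analysed is independent of the trigger. Trigger rates are assumed, at 180/240 mg. Odds ratios are medians in runs with a stop, shown with the stop against without it.

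| Trigger | Median first stop | On-drug | With placebo-level AEs |
|---|---|---|---|
| 13 dizziness discontinuations, rates 15%/20% | week 11 | 2.05 vs 2.63 | 2.42 vs 2.76 |
| 13 dizziness discontinuations, rates 10%/15% | week 14 | 2.34 vs 2.74 | 2.59 vs 2.82 |
| 2 syncopes, rates 2%/3% (stop in 98% of runs) | week 9 | 2.24 vs 2.99 | 2.53 vs 3.03 |

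The no-stop values in the dizziness rows are below 3.0 because individual discontinuations also shorten exposure.

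**The case against.** The strongest reply is that this is SAP detail. Section 12.2.4 has one sentence on the model, fixes neither the coding of dose nor the counting window, and section 12.2.1 promises a SAP before unblinding. A SAP could adjust for exposure, and that possibility stands. But the protocol foresees the terminated group, says what becomes of it in each analysis, and names an unadjusted model for data it keeps in. Followed as written, those rules give a biased slope. If dose is coded as a factor, the odds ratios of the stopped doses are understated instead.

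Second, section 12.2.1 speaks of safety presentations and does not name the AE regression, so inclusion of the stopped group is a reading. It is the natural one, given the safety set in 12.1.2.

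Third, the consequence is limited. The bias arises only once a dose and all above it have been stopped for safety, which already counts heavily against them, and the remaining doses are compared fairly. This stands and lowers the weight.

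Fourth, the AE risks, accrual and trigger rates are assumed, and section 6.4.3 collects AEs through follow-up, so an on-drug window is not the protocol's. With AEs counted to three weeks after a stop, the shifts in log odds ratio at weeks 8, 12 and 20 are ln(2.38/1.85) = 0.25, ln(2.38/1.99) = 0.18 and ln(2.38/2.13) = 0.11. Against a standard deviation of 0.39 for the logistic estimate at week 8, the first is about 0.25/0.39 = 0.6 SD. The bias is therefore moderate against sampling error, but it is systematic, and it was downward in every version computed.

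**Conclusion.** The concern holds, conditional on a safety stop and for AEs that arise over the treatment period. The direction follows from the protocol's own rules. The size depends on assumptions: for stops at weeks 8–20 with 180 and 240 mg terminated, a true odds ratio of 3.0 is expected to appear as 2.05–2.55 (on-drug AEs) or 2.42–2.73 (placebo-level AEs to week 4), and 2.38 appears as 1.73–2.13 when AEs are counted into follow-up. Stopping only 240 mg, or risk concentrated in week 1, reduces the error without removing it. The analysis supplements a descriptive safety objective and the stop may never occur, so this is a change that should be made, with medium confidence, and not a flaw in the main design.

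**What to change.** Keep the logistic regression and add to section 12.2.4:

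> If any dose group is terminated, a time-to-first-AE analysis by dose, censored at last dose, and exposure-adjusted rates will be reported beside the logistic regression.

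A suitable model is a discrete-time complementary log-log regression with a factor for visit interval, dose as regressor and log(days on IP in the interval) as offset. Working by visit interval lets it use actively questioned episodes, for which section 6.4.3.2 describes no start date. A Cox model is an alternative where start dates exist. With censoring at last dose, the result does not depend on how long AEs are counted after the stop.

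Under the same assumed risks the true hazard ratio is 0.288/0.105 ≈ 2.73. In 600 runs per setting, with 180 and 240 mg stopped at weeks 2–20, this model gave median hazard ratios of 2.71–2.85 under constant hazard and 2.64–2.87 with 70% of the risk in week 1, against 2.71–2.75 without a stop.

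The cost is one conditional sentence and a few lines of code. First and last dose dates (5.7) and AE start dates (6.4.3) are already recorded, and active questioning takes place at visits 2 to 7. The drawbacks are:

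- Hazard-type ratios will sit beside odds ratios.
- AEs after last dose are left to the crude tables.
- Actively questioned episodes between last dose and the end of treatment visit cannot be placed exactly.
- After a very early stop the estimate is less precise: SD of the log ratio 0.63 against 0.54 for the logistic model at week 2, but 0.37 against 0.39 at week 8.

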12.2.5 Interim analyses

No interim analysis of efficacy data will be performed. However, the DSMB will have the possibility to unblind treatment and evaluate safety data. See Section [5.4.2](#) and Section [12.4](#).

12.3 Determination of sample size

In the placebo-controlled study, [D9120C00027](#), with a similar patient population as in this study, the proportion of patients fulfilling the responder definition was 24% in the placebo group. Assuming a true placebo response rate of 24% and with 130 patients in each treatment group, a one sided Chi-square test at a significance level of 10% for the difference in proportion between dose and placebo group, will discover an increase of 15 percent points (ie the expected effect of the dose is assumed to be at least 39%) with an approximate power of

90%. This means that an observed difference of at least 8% will be statistically significant on the 10% level. The sample size has been calculated using nQuery, version 4.0.

Based on these calculations, 130 randomized patients per treatment group are considered to be sufficient to address the primary objective.

12.4 Data monitoring committees

Continuous safety surveillance of the study will be conducted as follows:

- The AstraZeneca representative (ICON) will provide weekly updates from participating countries to evaluate AEs and discontinuations due to AEs.
- A joint safety committee consisting of physicians and safety specialists from the AstraZeneca representative (ICON) and AstraZeneca will meet every second week to review blinded treatment data including adverse events (AEs, SAEs, DAEs), safety laboratory variables and orthostatic testing.
- An independent DSMB consisting of two physicians and a statistician will review/analyse preliminary data from a safety perspective to evaluate overall and specific safety parameters. The DSMB will be external to and independent from AstraZeneca and the AstraZeneca representative (ICON). The DSMB, will receive data regularly during the study and will have access to the randomization list. The DSMB alone will thus be able to do analyses on unblinded treatment data if necessary, see Section 5.4.1.

Safety reviews will be performed by the DSMB as defined in the charter. Included in the DSMB charter will be stopping criteria for either a single dose group or the whole study. The DSMB will continually survey DAEs and SAEs, and will review all of the safety data on at least two occasions during the study. The DSMB will remain available for extra meetings and analyses if potential safety concerns are identified by the joint safety monitoring committees of AstraZeneca and the AstraZeneca representative (ICON) or if the chairman of the DSMB deems it necessary for any reason.

Following each safety review, the DSMB will provide a recommendation regarding study continuation to the AstraZeneca representative (ICON). A decision body, which consists of the International coordinating investigator in the study, physicians and a statistician from AstraZeneca and a study physician at the AstraZeneca representative (ICON), will decide how to proceed with the study based on the DSMB recommendation.

13.2 Overdose

There is no data on overdosing. All intake of AZD3355 that exceeds the dosing described in the protocol is defined as an overdose.

- An overdose with associated AEs is recorded as the AE diagnosis/symptoms on the relevant AE modules in the eCRF and on the Overdose eCRF module.
- An overdose without associated symptoms is only reported on the Overdose eCRF module.

If an overdose on an AstraZeneca study drug occurs in the course of the study, then investigators or other site personnel inform appropriate AstraZeneca representative (ICON) within one day, ie, immediately but no later than the end of the next business day of when he or she becomes aware of it.

The designated AstraZeneca representative (ICON) works with the investigator to ensure that all relevant information is provided to the AstraZeneca Patient Safety data entry site.

For overdoses associated with SAE, standard reporting timelines apply, see Section 6.4.4. For other overdoses, reporting should be done within 30 days.

13.3 Pregnancy

All outcomes of pregnancy should be reported to AstraZeneca representative (ICON)

13.3.1 Maternal exposure

If a patient becomes pregnant during the course of the study IP should be discontinued immediately.

Pregnancy itself is not regarded as an AE unless there is a suspicion that the IP under study may have interfered with the effectiveness of a contraceptive medication. Congenital abnormalities/birth defects and spontaneous miscarriages should be reported and handled as SAEs. Elective abortions without complications should not be handled as AEs. The outcome of all pregnancies (spontaneous miscarriage, elective termination, ectopic pregnancy, normal birth or congenital abnormality) should be followed up and documented even if the patient was discontinued from the study.

If any pregnancy occurs in the course of the study, then investigators or other site personnel inform appropriate AstraZeneca representatives (ICON) **within one day** ie, immediately but no later than the **end of the next business day** of when he or she becomes aware of it.

The designated AstraZeneca representative (ICON) works with the investigator to ensure that all relevant information is provided to the AstraZeneca Patient Safety data entry site within 1 or 5 days for SAEs, see Section 6.4.4 and within 30 days for all other pregnancies.

The same timelines apply when outcome information is available.

The pregnancy module in the eCRF is used to report the pregnancy and the AstraZeneca representative (ICON) is responsible for providing reports of outcomes to the AstraZeneca Patient Safety data entry site and to inform the study team at AstraZeneca.

13.3.2 Paternal exposure

There is no restriction on fathering children or donating sperm during the study.

Appendix B
Additional Safety Information

FURTHER GUIDANCE ON THE DEFINITION OF A SERIOUS ADVERSE EVENT (SAE)

Life threatening

‘Life-threatening’ means that the subject was at immediate risk of death from the AE as it occurred or it is suspected that use or continued use of the product would result in the subject’s death. ‘Life-threatening’ does not mean that had an AE occurred in a more severe form it might have caused death (eg, hepatitis that resolved without hepatic failure).

Hospitalisation

Out-patient treatment in an emergency room is not in itself a serious AE, although the reasons for it may be (eg, bronchospasm, laryngeal oedema). Hospital admissions and/or surgical operations planned before or during a study are not considered AEs if the illness or disease existed before the subject was enrolled in the study, provided that it did not deteriorate in an unexpected way during the study.

Important medical event or medical intervention

Medical and scientific judgement should be exercised in deciding whether a case is serious in situations where important medical events may not be immediately life-threatening or result in death, hospitalisation, disability or incapacity but may jeopardize the subject or may require medical intervention to prevent one or more outcomes listed in the definition of serious. These should usually be considered as serious.

Simply stopping the suspect drug does not mean that it is an important medical event; medical judgement must be used.

Examples of such events are:

- Angioedema not severe enough to require intubation but requiring iv hydrocortisone treatment
- Hepatotoxicity caused by paracetamol (acetaminophen) overdose requiring treatment with N-acetylcysteine
- Intensive treatment in an emergency room or at home for allergic bronchospasm
- Blood dyscrasias (eg, neutropenia or anaemia requiring blood transfusion, etc) or convulsions that do not result in hospitalisation
- Development of drug dependency or drug abuse.

A GUIDE TO INTERPRETING THE CAUSALITY QUESTION

The following factors should be considered when deciding if there is a “reasonable possibility” that an AE may have been caused by the drug.

- Time Course. Exposure to suspect drug. Has the subject actually received the suspect drug? Did the AE occur in a reasonable temporal relationship to the administration of the suspect drug?
- Consistency with known drug profile. Was the AE consistent with the previous knowledge of the suspect drug (pharmacology and toxicology) or drugs of the same pharmacological class? OR could the AE be anticipated from its pharmacological properties?
- Dechallenge experience. Did the AE resolve or improve on stopping or reducing the dose of the suspect drug?
- No alternative cause. The AE cannot be reasonably explained by another aetiology such as the underlying disease, other drugs, other host or environmental factors.
- Rechallenge experience. Did the AE reoccur if the suspected drug was reintroduced after having been stopped? AstraZeneca would not normally recommend or support a rechallenge.
- Laboratory tests. A specific laboratory investigation (if performed) has confirmed the relationship?

A “reasonable possibility” could be considered to exist for an AE where one or more of these factors exist.

In contrast, there would not be a “reasonable possibility” of causality if none of the above criteria apply or where there is evidence of exposure and a reasonable time course but any dechallenge (if performed) is negative or ambiguous or there is another more likely cause of the AE.

In difficult cases, other factors could be considered such as:

- Is this a recognised feature of overdose of the drug?
- Is there a known mechanism?

Ambiguous cases should be considered as being a “reasonable possibility” of a causal relationship unless further evidence becomes available to refute this. Causal relationship in cases where the disease under study has deteriorated due to lack of effect should be classified as no reasonable possibility.

Clinical Study Protocol Appendix C

Drug Substance	AZD3355
Study Code	D9120C00019
Edition Number	01
Date	

